## 9.2 Secondary Endpoints

- 1) Proportion of patients positive for influenza virus titer (unit: %)
- Proportion of patients positive for influenza virus titer is defined as the percentage of patients whose virus titer is not less than the lower limit of quantification ( $0.7 \log_{10} \text{TCID}_{50}/\text{mL}$ ) among those assessed for virus titer on Days 2, 3, 4, 5, 6 and 9. Patients with a positive virus titer on Day 1 will be included in this analysis.

- 2) Proportion of patients positive by RT-PCR (unit: %)  
Proportion of patients positive by RT-PCR is defined as the percentage of patients with detectable virus RNA (2.05 for flu A and 2.83 for flu B  $\log_{10}$  vp/mL) among those assessed by RT-PCR on Days 2, 3, 4, 5, 6 and 9.  
Patients with a positive by RT-PCR on Day 1 will be included in this analysis.
- 3) Change from baseline in virus titer (unit:  $\log_{10}$ TCID50/mL)  
Change from baseline in virus titer is defined as the change from baseline in virus titer on Days 2, 3, 4, 5, 6 and 9. If virus titer is less than the lower limit of quantification, the virus titer will be imputed 0.7 (TCID50/mL).  
Patients with a positive virus titer on Day 1 will be included in this analysis.
- 4) Change from baseline in the amount of virus RNA (RT-PCR) (unit:  $\log_{10}$  virus particles/mL)  
Change from baseline in the amount of virus RNA is defined as the change from baseline in the amount of virus RNA on Days 2, 3, 4, 5, 6 and 9. If the amount of virus RNA is less than the lower limit of quantification and greater than or equal to the lower limit of detection, the amount of virus RNA will be imputed 2.18 for flu A and 2.93 for flu B ( $\log_{10}$  virus particles/mL). If the amount of virus RNA is less than the lower limit of detection, the amount of virus RNA will be imputed 2.05 for flu A and 2.83 for flu B ( $\log_{10}$  vp/mL). If a patient is infected with one virus type, the amount of virus RNA for infected virus type will be used for analysis. If a patient is infected with multiple virus types, the sum of those amount of virus RNA will be used for analysis. If the amount of virus RNA is missing for at least one of the multiple infected virus types collected on the same date, the amount of multiple virus RNA will be handled as missing at the corresponding date of assessment.  
Patients with a positive by RT-PCR on Day 1 will be included in this analysis.
- 5) Area under the curve adjusted by baseline in virus titer  
(unit:  $\log_{10}$ TCID50/mL×hours)  
This endpoint is defined as AUC of change from baseline in virus titer from Day 1 to Day 9. AUC is calculated using the trapezoidal method. AUC of change from time 0 ( $t_0$ ) to time  $K$  ( $t_K$ ) is given by the formula

$$\sum_{k=1}^K \frac{(y_k + y_{k-1} - 2y_0)(t_k - t_{k-1})}{2}$$

where  $t_k$  (hours) represents the date of the  $k^{\text{th}}$  viral titer assessment ( $k = 0, \dots, K$ ) and  $y_k$  represents the  $\log_{10}$  value of the  $k^{\text{th}}$  viral titer assessment (TCID50/mL). The lower limit is defined as 0.7 (TCID50/mL). One day is equal to 24-hours.  
Patients with a positive virus titer on Day 1 and available sample on Day 9 will be included in this analysis.

- 6) Area under the curve adjusted by baseline in the amount of virus RNA (RT-PCR) (unit:  $\log_{10}$  virus particles/mL $\times$ hours)  
This endpoint is defined as AUC of change from baseline in the amount of virus RNA (RT-PCR) from Day 1 to Day 9. The AUC is calculated using the same formula described in 'Area under the curve adjusted by baseline in virus titer'. The lower limit of quantification and greater than or equal to the lower limit of detection is defined as 2.18 for flu A and 2.93 for flu B ( $\log_{10}$  virus particles/mL). The amount of virus RNA is less than the lower limit of detection, the amount of virus RNA will be imputed 2.05 for flu A and 2.83 for flu B ( $\log_{10}$  vp/mL). If a patient is infected with one virus type, the amount of virus RNA for infected virus type will be used for analysis. If a patient is infected with multiple virus types, the sum of those the amount of virus RNA will be used for analysis. If the amount of virus RNA is missing for at least one of the multiple infected virus types collected on the same date, the amount of multiple virus RNA will be handled as missing at the corresponding date of assessment.  
Patients with a positive by RT-PCR on Day 1 and available sample on Day 9 will be included in this analysis.
- 7) Time to cessation of viral shedding by virus titer (unit: hours)  
This endpoint is defined as the time between the initiation of the study treatment and first time when the virus titer is below the limit of detection ( $0.7 \log_{10}$  TCID50/mL). Patients whose virus titer have not reached cessation by the last observation time point will treated as censored at that time point. One day is converted into 24 hours.  
Patients with a positive virus titer on Day 1 will be included in this analysis.
- 8) Time to cessation of viral shedding by RT-PCR (unit: hours)  
This endpoint is defined as the time between the initiation of the study treatment and first time when the virus RNA by RT-PCR is below the limit of detection. Patients whose virus RNA have not reached cessation by the last observation time point will treated as censored at that time point. For the patients with multiple virus types, this endpoint is defined as the time between the initiation of the study treatment and first time when the virus RNA by RT-PCR is below the limit of detection for all virus types. One day is converted into 24 hours.  
Patients with a positive virus RNA on Day 1 will be included in this analysis.
- 9) Proportion of patients whose symptoms have been alleviated (unit: %)  
This endpoint is defined as the percentage of patients whose symptoms have been alleviated at 12, 24, 36, 48, 72, 96, 120, 144, 168, 192 and 216 hours after the initial of study treatment. The alleviation of symptoms is defined as the time when all of 7 symptoms have been assessed by the patient as 0 (None) or 1 (Mild) in the patient eDiary.
- 10) Time to alleviation of the 4 systemic symptoms (unit: hours)  
The endpoint is the time to alleviation of the 4 systemic symptoms (headache, feverishness or chills, muscle or joint pain, and fatigue), which is defined as the

time between the initiation of the study treatment and the alleviation of influenza symptoms. The alleviation of the 4 symptoms is defined as the time when all of the 4 systemic symptoms have been assessed by the patient as 0 (None) or 1 (Mild) in the patient eDiary, for a duration of at least 21.5 hours (24 hours – 10%).

Patients who do not experience alleviation of symptoms by the last observation time point will be censored at that time point. If at least one of the 4 influenza symptom scores is missing at date and time of assessment that patients have, missing assessments of influenza symptoms conservatively will be treated as having moderate or severe symptoms (as failures) at the corresponding date and time of assessment.

11) Time to alleviation of the 3 respiratory symptoms (unit: hours)

The endpoint is the time to alleviation of the 3 respiratory symptoms (cough, sore throat, and nasal congestion), which is defined as the time between the initiation of the study treatment and the alleviation of influenza symptoms. The alleviation of the 3 symptoms is defined as the time when all of the 3 respiratory symptoms have been assessed by the patient as 0 (None) or 1 (Mild) in the patient eDiary, for a duration of at least 21.5 hours (24 hours – 10%). Patients who do not experience alleviation of symptoms by the last observation time point will be censored at that time point. If at least one of the 3 influenza symptom scores is missing at date and time of assessment that patients have, missing assessments of influenza symptoms conservatively will be treated as having moderate or severe symptoms (as failures) at the corresponding date and time of assessment.

12) Time to alleviation of individual symptoms (unit: hours)

Time to alleviation of cough symptom is defined as the time from the start of treatment to the start of the time period when cough symptom have been assessed by the patient as 0 (None) or 1 (Mild) in the patient eDiary, for a duration of at least 21.5 hours (24 hours – 10%). The following endpoints are defined in a similar way. Patients who do not experience alleviation of symptoms by the last observation time point will be censored at that time point. If symptom score is missing at date and time of assessment that patients have, missing assessment of influenza symptom conservatively will be treated as having moderate or severe symptoms (as failures) at the corresponding date and time of assessment.

Patients whose symptom at baseline is assessed as 0 (None) or 1 (Mild) will be excluded from the analysis.

- Time to alleviation of sore throat symptom
- Time to alleviation of headache symptom
- Time to alleviation of nasal congestion symptom
- Time to alleviation of feeling feverish or having chills symptom
- Time to alleviation of aches and pains of the muscle or joints symptom
- Time to alleviation of fatigue symptom

13) Change from baseline in composite symptom score

This endpoint is defined as the change from baseline in the total score of 7 influenza symptoms (cough, sore throat, headache, nasal congestion, feverishness or chills, muscle or joint pain, and fatigue) as assessed by the patient in the patient eDiary at 12, 24, 36, 48, 72, 96, 120, 144, 168, 192 and 216 hours. “None”, “Mild”, “Moderate” and “Severe” will be scored as 0, 1, 2 and 3, respectively. If at least one of the 7 influenza symptom scores is missing at date and time of assessment that patients have, composite symptom score will be handled as missing at the corresponding date and time of assessment.

14) Time to resolution of fever (unit: hours)

Time to resolution of fever is defined as the time between the initiation of the study treatment and the resolution of fever. The resolution of fever is defined as the time when the patient’s self-measured axillary temperature becomes less than 37°C and is maintained at less than 37°C for duration of at least 12 hours. Patients who do not experience resolution of fever by the last observation time point will be censored at that time point. If body temperature is missing at date and time of assessment that patients have, missing assessments of body temperature conservatively will be treated as having more than 37 °C (as failures) at the corresponding date and time of assessment. Patients whose body temperature at baseline is less than 37°C will be excluded from the analysis. Body temperature obtained when e-diary is set up after initial dosing will not be used for analysis. Because these data may be observed due to e-dairy system’s incorrect setting.

15) Proportion of patients reporting normal temperature (unit: %)

Proportion of patients reporting normal temperature is defined as the percentage of patients whose axillary temperature drops to less than 37°C after the initiation of the study treatment at 12, 24, 36, 48, 72, 96, 120, 144, 168, 192 and 216 hours. Body temperature obtained when e-diary is set up after initial dosing will not be used for analysis. Because these data may be observed due to e-dairy system’s incorrect setting.

Patients whose body temperature at baseline is less than 37°C will be excluded from the analysis.

16) Body temperature (unit: degree)

Body temperature is defined as measured axillary temperature at 12, 24, 36, 48, 72, 96 and 120 hours. Body temperature obtained when e-diary is set up after initial dosing will not be used for analysis. Because these data may be observed due to e-dairy system’s incorrect setting.

17) Time to return to preinfluenza health status (unit: hours)

Patients will be asked to record their preinfluenza health status between 0 (worst possible health) and 10 (normal health [for someone your age and your health condition]). Time to return to preinfluenza health status is defined as the time from the initiation of the study treatment to the first time when health status score is equal to or higher than the preinfluenza health status score. Patients who have

smaller number on scale for preinfluenza health status by the last observation time point will be censored at that time point. If preinfluenza health status is missing at date and time of assessment that patients have, missing assessments of preinfluenza health status conservatively will be treated as having less than preinfluenza health status at the corresponding date and time of assessment.

Patients whose health status score at baseline is equal to or higher than the preinfluenza health status score will be excluded from the analysis. Health status score obtained when e-diary is set up after initial dosing will not be used for analysis. Because these data may be observed due to e-dairy system's incorrect setting.

18) Incidence of influenza-related complications (unit: %)

This endpoint is defined as the percentage of patients who experience each influenza-related complication (hospitalization, death, sinusitis, otitis media, bronchitis, and radiologically confirmed pneumonia) as an AE after the initiation of the study treatment. A specific complication eCRF with diagnostic criteria for the complications of sinusitis, otitis media, bronchitis and pneumonia will be provided as following rules.

- Sinusitis
  - 'Sinusitis' in the 'Form Incidence of influenza-related complications' is 'Yes'
  - And 'Did these symptoms start after the influenza treatment was given on Day 1?' in the 'Form Sinusitis' is 'Yes'
  - And 'Does the patient have a purulent nasal discharge?' in the 'Form Sinusitis' is 'Yes'
  - And 'Does the patient have facial pain, pressure sensation, or sensation of fullness?' in the 'Form Sinusitis' is 'Yes'
  - And 'Does the patient have nasal obstruction, congestion or stuffiness?' in the 'Form Sinusitis' is 'Yes'
- Otitis media
  - 'Otitis media' in the 'Form Incidence of influenza-related complications' is 'Yes'
  - And 'Did these symptoms start after the influenza treatment was given on Day 1?' in the 'Form Otitis Media' is 'Yes'
  - And 'Does the patient have pain or fullness in one or more ears?' in the 'Form Otitis Media' is 'Yes'
  - And 'Does the patient have tympanic membrane bulging or fullness on otoscopy?' in the 'Form Otitis Media' is 'Yes'
- Bronchitis
  - 'Bronchitis' in the 'Form Incidence of influenza-related complications' is 'Yes'

- And ‘Did these symptoms start after the influenza treatment was given on Day 1?’ in the ‘Form Bronchitis’ is ‘Yes’
- And ‘Does the subject have a productive cough that has got worse after Day 1?’ in the ‘Form Bronchitis’ is ‘Yes’
- Pneumonia
  - ‘Pneumonia’ in the ‘Form Incidence of influenza-related complications’ is ‘Yes’
  - And ‘Did these symptoms start after the influenza treatment was given on Day 1?’ in the ‘Form Pneumonia’ is ‘Yes’
  - And ‘Does the patient have worsening cough since starting study treatment?’ in the ‘Form Pneumonia’ is ‘Yes’
  - And ‘Does a Chest X Ray confirm pneumonia i.e. consolidation?’ in the ‘Form Pneumonia’ is ‘Yes’

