**Table 2-2 Acceptable Time Windows for Parameters Other than Data from the Patient Diary**

Time Point	Acceptable Time Window
Pre-dose at Visit 1 (Day 1: Day -2 to Day1)	Predose from Day -2 to Day 1 for safety assessment
Pre-dose at Visit 1 (Day 1)	Predose on Day 1 for efficacy assessment
Post-dose at Visit 1 (Day 1)	QOL assessment with EQ-5D-5L questionnaire: by 0.5 hour post-dose on Day 1 Other measurements: 0.5 to 4 hours post-dose on Day 1
Visit 2 (Day 2)	Day 2
Visit 3 (Day 3)	Between Day 3 and Day 4
Optional-Visit 1 (Day 4)	Day 4
Visit 4 (Day 5)	Between Day 5 and Day 6
Optional Visit 2 (Day 6)	Day 6
Visit 5 (Day 9)	Between Day 7 and Day 11
Visit 6 (Day 15)	Between Day 12 and Day 18
Visit 7 (Day 22)	Between Day 19 and Day 25
Early termination	Date of early termination + 3 days

Measurements collected within the acceptable time window for each scheduled assessment time point, including data obtained at the time of withdrawal, will be used for the analyses of all endpoints at each assessment time point. For all patients with multiple measurements within a visit window, the measurement obtained closest to the target time point will be used. If two measurements collected with the same time deviation exist before and after the target time point, the measurement obtained before the target time point will be adopted for analysis. The assessment time point having no measurements within the corresponding acceptable time window will be considered as missing.

In the patient diary, if there are multiple measurements which may be adopted for a scheduled assessment, even though the above rules have been strictly followed, the measurements of the earlier assessment date or the earlier assessment time of day will be adopted (with the priority given to morning, followed by afternoon, evening, and bedtime, in this order). If multiple measurements collected with the same time (date and hour) for body temperature, the highest measurement will be adopted.

In the assessment of items from other than the patient diary, if there are multiple measurements which may be adopted for a scheduled assessment time point (even though the above rules have been strictly followed), the measurements at the time point entered in the CRF will be adopted.

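### The viral AUC is not divided by follow-up time, although its last swab may fall anywhere from Day 7 to Day 11, so attendance day adds avoidable noise to this secondary endpoint

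*SAP*

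**What the plan says.** SAP 9.2 item 5) states: "This endpoint is defined as AUC of change from baseline in virus titer from Day 1 to Day 9". It adds: "AUC is calculated using the trapezoidal method". The formula sums (y_k + y_{k−1} − 2y_0)(t_k − t_{k−1})/2 over the assessments. The time variable is described with the words "hours) represents the date of the" k-th titer assessment, and the conversion is "One day is equal to 24-hours". The sum is not divided by (t_K − t_0), and the endpoint's unit remains log10 × hours. Item 6) applies the same formula to viral RNA.

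Each AUC has an entry condition. For titer: "Patients with a positive virus titer on Day 1 and available sample on Day 9 will be included in this analysis". For RNA: "Patients with a positive by RT-PCR on Day 1 and available sample on Day 9 will be included in this analysis".

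SAP Table 2-2 gives the window for Visit 5 (Day 9) as "Between Day 7 and Day 11", and Protocol Table 7-6 agrees. With several swabs in one window, "the measurement obtained closest to the target time point will be used". A single off-target swab still serves as the Day 9 value.

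Both AUCs are compared by van Elteren test, against placebo and against oseltamivir (Protocol 9.10.3.2; SAP 9.4 item 3). Neither document cuts the AUC at a common time, averages it over time, or plans a sensitivity analysis for it.

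**The concern.** An AUC that is not divided by time grows with the length of the interval. Once a patient's titer is at the floor of 0.7, every further day before the last swab adds a full day of that patient's maximum change. Two patients with the same viral course then get different values, and different ranks, because one came on Day 7 and the other on Day 11. The stake is precision in both treatment comparisons. The variation comes from appointment scheduling and carries no information about the drug.

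**Working it through.** The documents give no SD, effect size or power for the viral AUC, so there is no plan figure to reproduce. The check has an exact part, which follows from the SAP formula, and an illustrative part, which needs assumptions.

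**Length of the interval.** With Day 1 as time 0 and 24 h per day, a last swab on Day 7 gives t_K = 6 × 24 = 144 h, Day 9 gives 8 × 24 = 192 h, and Day 11 gives 10 × 24 = 240 h. The range is 240/144 = 1.67-fold.

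**One viral course, three attendance days.** Take illustrative titers of 5.7, 3.2, 1.7 and 0.7 at 0, 24, 48 and 96 h, staying at 0.7. The changes are 0, −2.5, −4.0 and −5.0.

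- Up to 96 h: 24 × (−2.5)/2 + 24 × (−6.5)/2 + 48 × (−9.0)/2 = −30 − 78 − 216 = −324.
- After 96 h: −5.0 × (t_K − 96).

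| Last swab | AUC as written | AUC / t_K | AUC to fixed 192 h |
|---|---|---|---|
| Day 7 | −324 − 240 = −564 | −3.92 | −804 |
| Day 9 | −324 − 480 = −804 | −4.19 | −804 |
| Day 11 | −324 − 720 = −1044 | −4.35 | −804 |

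As written, the AUC moves by 240/804 = 30% in each direction. Divided by t_K, it moves by about 6% one way and 4% the other. The fixed 192 h column interpolates when the last swab is later and carries the last value when it is earlier.

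**Effect on variance.** The following are assumptions, not figures from the documents:

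- baseline titer normal, mean 5 and SD 1.2;
- floor 0.7 (this one is in the SAP);
- linear decline to the floor, with gamma-distributed time to floor, mean 72 h and shape 4;
- swabs on Days 1, 2, 3 and 5, plus one on Day 7 to 11.

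In the simulation the mean AUC is about −658.

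| Spread of last swab | SD of AUC | Variance ratio | Loss of effective n (1 − 1/ratio) |
|---|---|---|---|
| All on Day 9 | 202 | 1.00 | 0% |
| 90% on Day 9, 2.5% on each other day | 209 | 1.06 | 6% |
| 80% on Day 9, 5% on each other day | 216 | 1.13 | 12% |
| 5/15/60/15/5% over Days 7–11 | 221 | 1.19 | 16% |
| Even over Days 7–11 | 251 | 1.54 | 35% |

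A hand check agrees. Each day of delay adds 24 × (final change), and the mean squared final change is about 4.3² + 1.2² = 19.93. The added variance is therefore about 24² × 19.93 = 11,480 × Var(visit day). Var(visit day) is 0.7 for the 60% case and 2.0 for the even case. Against 202² = 40,804 this gives ratios of 1 + 8,036/40,804 = 1.20 and 1 + 22,960/40,804 = 1.56.

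The coefficient of variation of the AUC is 0.31 with all swabs on Day 9, 0.34 in the 60% case and 0.38 in the even case. For the time-weighted average it stays at 0.31 throughout.

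**Effect on a rank test.** A second assumed model used linear decline with a group difference in rate, 412 v 206 patients, and an unstratified Wilcoxon test standing in for van Elteren. Efficiency of the AUC as written, relative to the fixed 192 h AUC, was 0.75 to 0.86 with 60% of last swabs on Day 9 and 0.49 to 0.66 with an even spread. With mean baseline 5.5 and SD 1.5, power was about 97% for either alternative, against 94% (60% case) and 85% (even case) as written. Simulated type I error stayed between 4.2% and 6.5%.

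**The case against.** **Nominal days are possible.** The endpoint is labelled Day 1 to Day 9, an in-window swab becomes the Day 9 value, and time is counted in whole days. A programmer could set t_K to 192 h for everyone. The reference to the date of each assessment points the other way, but the reading is not excluded. It would remove the varying length and misplace off-day swabs instead. The point is therefore conditional, and the SAP should say which applies.

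**The size is hypothetical.** The documents give neither titer distributions nor the spread of Day 9 visits. An even spread treats Day 9 as no target at all. This stands: the percentages illustrate, and the range must start at zero.

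**The Day 9 sample rule has a rationale.** The last swab scheduled for every patient before Day 9 is on Day 5; Day 6 is optional. Without a late sample, an AUC to Day 9 needs extrapolation, and SAP 6.4 rules out imputation. The other titer and RNA endpoints carry no such condition, so earlier swabs are still analysed there. A reader might infer that the rule selects completers and biases the comparison. That is possible, but the documents give no missingness figure to support it.

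**Relaxing the rule would do harm.** A reader might also infer that anyone with one post-baseline swab should enter a time-averaged analysis. Take a linear fall of 4.3 log10, reaching the floor at 72 h. For this one viral course the trapezoidal time average is −0.72 if the last swab is on Day 2, −1.43 on Day 3, −2.51 on Day 5 and −3.40 on Day 9. That 4.7-fold spread exceeds the 1.67-fold range of t_K at issue here. Early leavers would rank as poor responders.

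**Conclusion.** The point holds as a matter of precision, provided actual dates are used. The formula then integrates over 144 to 240 h, and identical viral courses receive different ranks. Under the first set of assumed curves the loss of effective sample size is 0% if all last swabs fall on Day 9, about 16% if 60% do, and about 35% under an even spread. The second model gives larger losses for the same spreads, which shows how far the figure depends on assumptions.

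The documents do not support reading this as bias or as a threat to the trial's conclusions. In a blinded trial attendance day should be similar across groups, and simulated type I error stayed near 5%. The hierarchy in SAP 6.2 covers only the primary endpoint, so neither of its comparisons is touched. This is a cheap improvement, not a necessary correction.

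**What to change.** In SAP 9.2 items 5) and 6), state that t_k is the actual assessment date. Then, keeping the Day 9 sample condition, do one of the following:

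- Divide the AUC by (t_K − t_0) and report a time-weighted average change from baseline.
- Evaluate the AUC to a fixed 192 h, with a written rule for later last swabs (for example interpolation) and earlier ones (for example carrying the last value).

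The first is a one-line change. Its cost is a new unit (log10 rather than log10 × hours) and a small remaining dependence on visit day. The second keeps the unit and, under the example rule, removes the dependence for patients already at the floor. Carrying a value forward would, however, need an explicit exception to the no-imputation rule in SAP 6.4. Neither option needs new data, and either can be made before unblinding. Do not extend the time-averaged analysis to patients with only one post-baseline swab.

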3. INVESTIGATIONAL PLAN

3.1 Overall Study Design and Plan

This study is a randomized, double-blind, multicenter, parallel-group, placebo- and active-controlled study designed to evaluate the efficacy and safety of single dose of S-033188 in otherwise healthy adult and adolescent patients with influenza virus infection.

Prior to the initiation of the study treatment on Day 1, patients will be assessed for eligibility for participation in the study. Patients aged 20 to 64 years who are determined to be eligible will be randomly assigned in a ratio of 2:2:1 to receive a single dose of S-033188 (either 40 mg or 80 mg according to weight), 75 mg BID of oseltamivir for 5 days, or placebo. Patients aged 12 to 19 years who are determined to be eligible will be randomly assigned in a ratio of 2:1 to receive a single dose of either 40 or 80 mg of S-033188 or placebo. Patients who weigh < 80 kg at Screening will receive 40 mg of S-033188, and patients who weigh ≥ 80 kg at Screening will receive 80 mg of S-033188. The study drug will be administered orally at the study center on Day 1 (initial dose). Patients aged 20 to 64 years will receive study drug twice daily for 5 days in total. For patients aged 12 to 19 years, a single dose of study drug will be tested. There is a maximum of 9 visits including 2 optional visits during a period to assess the efficacy and safety: 14 days for efficacy and 22 days for safety. The study schematic is shown in Figure 3-1. The time and events schedule is provided in Appendix 1.

Figure 3-1 Study Schematic

This study will be conducted in compliance with this protocol, International Conference on Harmonisation-Good Clinical Practices (ICH-GCPs), and all applicable requirements.

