7.4.2 Virology Test

Two nasopharyngeal/pharyngeal swabs (nasopharyngeal swabs are the preferred method of virology collection as they are the most accurate, but pharyngeal swabs will be acceptable if nasopharyngeal swabs cannot be performed) will be collected predose at Visit 1 (Day 1 at the same time as the RIDT), Visit 2 (Day 2), Visit 3 (Day 3), Visit 4 (Day 5) and Visit 5 (Day 9). If circumstances permit, specimens will also be collected at Optional Visit 1 (Day 4) and Optional Visit 2 (Day 6) and Visit 7 (Day 22). If the investigator or subinvestigator determines that influenza symptoms are ongoing, specimens will also be collected at Visit 6 (Day 15) and Visit 7 (Day 22) (or early termination). Specimens will be handled according to Section 7.6.4.5.

The virology testing facility (see Section 10.1) will perform virus typing and subtyping, determination of virus titer and viral RNA load according to procedures or a protocol specified in a separate document. Access to the virological endpoints will be limited. Specific details of who will have access to each endpoint will be specified in a separate document.

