- c The patient will measure or assess and record in the patient eDiary, body temperature 4 times daily (morning, noon, evening, and bedtime) from Days 1 to 3 and twice daily (morning and evening) from Days 4 to 14; severity of influenza symptoms twice daily (morning and evening) from Days 1 to 9 and once daily (evening) from Days 10 to 14; assessment of health once daily (evening) from Days 1 to 14; and EQ-5D-5L twice daily (morning and evening) from Days 1 to 9 and once daily (evening) from Days 10 to 14.
- d Predose, if the study treatment is initiated at 18:00 or later on Day 1, the patient will not need to perform Day 1 evening assessments.
- e Body weight will be measured.
- f Height will be measured in the predose examinations only.
- g Urine pregnancy test will be performed only for females who are not diagnosed as postmenopausal.
- h Predose.
- i Virology swabs will be collected if investigator determines that flu symptoms are persisting.
- j Virology swabs will be collected at the early termination.
- k Blood samples will be collected for the measurement of plasma drug concentrations at Visits 2 (Day 2) and 4 (Day 5). If circumstances permit, samples will also be collected at 0.5 to 4 hours post-dose at Visit 1 (Day 1), and at Visit 3 (Day 3) and Visit 6 (Day 15).

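### Time to cessation of viral shedding has no Day 9 limit, so its Kaplan-Meier curve beyond Day 9 rests mainly on patients who still have symptoms and can overstate shedding

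*SAP*

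**What the plan says.** **Who is swabbed.** Protocol 7.4.2 schedules swabs for every patient before dosing on Day 1 and then at "Visit 2 (Day 2), Visit 3 (Day 3), Visit 4 (Day 5) and Visit 5 (Day 9"). Two further groups of swabs are conditional:

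- Days 4 and 6: "If circumstances permit, specimens will also be collected at Optional Visit 1 (Day 4) and Optional Visit 2 (Day 6"). No symptom condition is attached. Protocol 3.1 says only: "There is a maximum of 9 visits including 2 optional visits".
- Days 15 and 22: "If the investigator or subinvestigator determines that influenza symptoms are ongoing, specimens will also be collected at Visit 6 (Day 15"), with Day 22 or early termination under the same condition. The Appendix 1 footnote agrees: "Virology swabs will be collected if investigator determines that flu symptoms are persisting". Section 7.4.2 also names Day 22 among the swabs taken when circumstances allow. Appendix 1 does not, and the two should be reconciled.

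**What is analysed.** In SAP 9.2 items 7) and 8) the event is the first result below the limit. The censoring rule for titer is: "Patients whose virus titer have not reached cessation by the last observation time point will treated as censored at that time point". Nothing restricts this to scheduled visits or to Day 9. SAP 9.4 item 4) then applies the primary-endpoint methods: stratified Peto-Prentice test, Kaplan-Meier curve, medians, and a bootstrap interval for the difference in medians.

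The other virology endpoints stop at Day 9. The proportion positive is taken "among those assessed for virus titer on Days 2, 3, 4, 5, 6 and 9" and, for RNA, "among those assessed by RT-PCR on Days 2, 3, 4, 5, 6 and 9". Change from baseline uses the same days. The AUC endpoints run from Day 1 to Day 9 and require a Day 9 sample. SAP 6.4 imputes nothing, and no sensitivity analysis is planned for shedding.

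**The concern.** A patient still positive at Day 9 who has recovered usually gives no further swab and is censored there. One who is still ill is swabbed again and carries the curve forward. Kaplan-Meier estimation assumes that those censored would have cleared at the same rate as those followed. If slow symptom recovery goes with slow viral clearance, that assumption fails and the curve after Day 9 is too high. Symptom status at that point is itself affected by treatment, so the error need not be equal in the two arms.

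A smaller question concerns Days 4 and 6. Those swabs depend on attendance after randomisation, and the SAP tests each day among whoever was assessed. If the recovered stay away, the sampled groups are no longer the randomised groups.

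At stake is the description of shedding, RNA in particular, and the reading of the Day 4 and Day 6 comparisons.

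**Working it through.** **From the documents.** Median time to alleviation 72 h on S-033188 and 100 h on placebo, exponential (Protocol 9.2); 412 v 206 ITTI patients; two-sided 0.05. Under these assumptions the planned 618 patients reproduce (90.03% power with Gehan weights and 336 h follow-up). The documents give no figure for shedding or for optional attendance.

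**Assumed.** Lognormal clearance time T, identical in both arms. Symptom time S is linked to T by a normal correlation. Nominal times are 192 h for Day 9 and 336 h for Day 15.

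**Late swabs.** At Day 15 only patients with S > 336 are swabbed, so the curve estimates

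KM(Day 15) = P(T > 192) × P(T > 336 | T > 192, S > 336),

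while the truth is P(T > 192) × P(T > 336 | T > 192).

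For an RNA median of 192 h and log-SD 0.5:

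- P(T > 192) = 0.50.
- P(T > 336) = 1 − Φ(ln(336/192)/0.5) = 1 − Φ(1.119) = 0.132, so the true conditional probability is 0.132/0.50 = 0.263.
- Still symptomatic at 336 h: 2^(−336/72) = 3.9% on S-033188 and 2^(−336/100) = 9.7% on placebo.
- At correlation 0.5 the conditional probability among those swabbed is 0.542 on S-033188 and 0.470 on placebo (bivariate normal).
- KM(Day 15) = 0.50 × 0.542 = 27% and 0.50 × 0.470 = 23%, against a true 13% in both arms.

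The same formula with other assumptions, log-SD 0.5:

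| Clearance median | Correlation | Day 15 curve, S-033188 / placebo | Truth |
|---|---|---|---|
| 96 h | 0.5 | 1.2% / 1.0% | 0.6% |
| 192 h | 0 | 13% / 13% | 13% |
| 192 h | 0.3 | 21% / 19% | 13% |
| 192 h | 0.5 | 27% / 23% | 13% |
| 240 h | 0.5 | 47% / 43% | 25% |

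The error vanishes without correlation and is negligible if nearly all patients clear by Day 9. It matters for slow clearance, which is more plausible for RNA than for titer. The formula ignores Day 22 swabs from recovered patients. Such a patient counts as at risk and not yet negative at Day 15, which would push the curve up further.

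**Effect on the test.** With the 192 h median and correlation 0.5, simulated null rejection of the Peto-Prentice test is 5–6%. The late swabs distort the estimate and hardly touch the test.

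**Days 4 and 6.** First, how far can attendance differ by arm? Suppose only ill patients attend. At 72 h attendance is 2^(−72/72) = 50% v 2^(−72/100) = 61%; at 120 h it is 2^(−120/72) = 32% v 2^(−120/100) = 44%. The largest gap is therefore 11–12 points.

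Simulated null rejection rates with no viral effect, using clearance medians from 48 to 96 h and, for the last row, 72 h:

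| Correlation | Attendance, ill / recovered | Cessation test | Day 4 and 6 tests |
|---|---|---|---|
| 0.5 | 60% / 30% to 100% / 0% | about 5–7% | about 5–12% |
| 0.8 | 90% / 10% | about 9–9.5% | about 14–15% |

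A run of 700 trials at the most extreme correlation-0.5 setting gave 8.1% for the cessation test, with a Monte Carlo standard error of about 1 point. With correlation 0.8 and attendance by the ill only, the Day 4 and Day 6 tests reach 26–34%. When the ill attend more, most of the excess rejections go against S-033188. Using only the scheduled Day 2, 3, 5 and 9 swabs returns the cessation test to about 5–6%.

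**The case against.** The best reply is that the endpoint rests mostly on swabs scheduled for everyone, that its test nearly keeps its level, and that any error mainly disadvantages the sponsor's own drug. All three points stand. The type I error hierarchy in Protocol 9.1 and SAP 6.2 covers only time to alleviation, against placebo and then oseltamivir. The proportion-positive and change-from-baseline endpoints are also tested on Days 2, 3, 5 and 9. Censoring at Day 9 also discards real information on later RNA clearance.

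A reader might infer something stronger: that patients are sampled on Days 4 and 6 according to recovery, and that the cessation test is therefore badly inflated. The documents do not support this. Protocol 7.4.2 attaches a symptom condition only to the late swabs; recovery-driven attendance on Days 4 and 6 is conjecture. Serious inflation of the cessation test would need a gap in attendance between arms of 30 points or more, whereas the planning medians allow 11–12 even if nobody who has recovered attends. The study is also double-blind.

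What the reply does not answer is the late curve. SAP 9.4 item 4) plans curves, medians and intervals for this endpoint, and a test that keeps its level does not make those estimates right.

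**Conclusion.** The point holds as a minor one. The text facts are certain: late swabs depend mainly on symptoms, and time to cessation has no Day 9 limit although endpoints 1) to 6) do. The consequence is conditional. With slow RNA clearance and positive correlation between recovery and clearance, the curve beyond Day 9 is too high, by roughly a factor of two at Day 15 in the central example. That size depends on the assumed median, spread and correlation, none of which the documents give. For fast clearance or zero correlation there is nothing to correct.

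For Days 4 and 6 the concern is about transparency. Material inflation needs both strong dependence of attendance on recovery and strong correlation of recovery with clearance. The primary conclusion is unaffected.

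**What to change.** 1. In SAP 9.2 items 7) and 8) and 9.4 item 4), censor patients not yet negative at the Visit 5 (Day 9) swab, or at their last earlier swab if Visit 5 is missing. State which swabs count.
2. Add an analysis that uses only the Visit 2, 3, 4 and 5 swabs, or an interval-censored analysis. Select swabs by visit label, because the Visit 3 and Visit 4 windows (SAP Table 2-2) extend to Days 4 and 6. Step 1 alone leaves the optional swabs in the main analysis, so this step is what checks their influence.
3. Report the number sampled on Days 4 and 6 by arm, and treat comparisons on those days as descriptive.
4. Reconcile the condition for the Day 22 swab between Protocol 7.4.2 and Appendix 1.

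The cost is a few sentences in the SAP and a filter on visit. Later RNA clearance data leave the main analysis, and event times are slightly coarser in the scheduled-visit analysis. In one simulation (350 v 350, assumed clearance medians 60 v 70 h, equal attendance) dropping the optional swabs lowered power from 86.7% to 85.9%.
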